6.1.1. General Considerations for Analyses during the Blinded Treatment Dosing Period (Period 2)

Comparisons between ixekizumab regimen 80 mg Q4W and placebo will be performed for all analyses in Period 2.

Period 2 starts at the first injection of study treatment at Week 0 (Visit 2) and ends prior to the first injection of study treatment at Week 16 (Visit 8) or the ETV (between Weeks 0 and 16). If a patient has Visit 8 but does not receive injection at Week 16 (Visit 8), the last recorded time for Visit 8 is used as the end time for Period 2.

Baseline will be defined as the last available value before the first injection for efficacy, health outcome, and safety analyses. In most cases, this will be the measure recorded at Week 0 (Visit 2). For efficacy measures, if the patient does not take any injection, the last available value on or prior to randomization date will be used. Change from baseline will be calculated as the visit value of interest minus the baseline value. For safety analyses using a baseline period, the baseline period is defined as the time from Visit 1 to the date/time of the first injection.

The randomization to treatment groups is stratified by baseline CRP status (nonelevated versus elevated) and TNF inhibitors experience (experienced or naïve) as described in Section 5.2. Unless otherwise specified, the statistical analysis models will adjust for baseline CRP status, and prior TNF inhibitors experience(if applicable).

The primary analysis method for treatment comparisons of categorical efficacy and health outcomes variables at specific time points will be made using a logistic regression analysis with treatment, baseline CRP status, and TNF inhibitors experience (if applicable) in the model. The proportions, odds ratio and 95% confidence intervals (CIs) will be reported; treatment difference and 95% CIs will also be reported. Secondary analysis will be conducted using a Fisher's exact test. In the case when logistic regression model does not produce statistical results due to sparse data, Fisher's exact test will be used.

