Maastricht Ankylosing Spondylitis Enthesitis Score (MASES): The MASES is an index used to measure the severity of enthesitis (Heuft-Dorenbosch et al. 2003). The MASES assesses 13 sites for enthesitis using a score of “0” for no activity, or “1” for activity. Sites assessed include: costochondral 1 (right/left), costochondral 7 (right/left), spinal iliaca anterior superior (right/left), crista iliaca (right/left), spinal iliaca posterior (right/left), processus spinosus L5, and Achilles tendon proximal insertion (right/left).	MASES	The MASES is the sum of all site scores. Range: 0 to 13, higher scores indicate more severe enthesitis 0 = no activity and not evaluable 1 = activity	Missing if >20% (ie, ≥3) sites are missing. If ≤20% missing, then imputed sum = sum of scores from nonmissing sites x 13/ no. of nonmissing sites
	MASES score = 0	MASES score = 0 refers to complete resolution in enthesitis. Analysis of MASES score = 0 only applies to patients with baseline enthesitis (MASES >0).	Missing if observed value is missing
	Heel Enthesitis score = 0	Heel Enthesitis score = 0 refers to Achilles tendon proximal insertion (right/left) = 0. Analysis of Heel Enthesitis score = 0 only applies to patients with baseline Heel Enthesitis score >0.	Missing if observed value is missing

Measure / Description	Variable	Derivation / Comment	Imputation Approach if with Missing Components
Non-Steroidal Anti-Inflammatory Drug (NSAID) Intake: Information regarding NSAIDs (including COX-2 inhibitors) intake will be collected in the eCRF and the ASAS-NSAID score will be calculated (Dougados et al. 2011).	Proportion of patients taking NSAID	Proportion of patients taking NSAID (including COX-2 inhibitors) at specified visit	NA
	ASAS -NSAID score	See Section 6.9.4.1 and Appendix 2 for details of deriving ASAS-NSAID score. ASAS-NSAID = 0 if no NSAID use	If NSAID dose is missing, the maximum efficacy dose (Appendix 2) is assumed. If frequency is missing, 'every day' intake is assumed.
	ASAS-NSAID50	$100 \times \frac{\text{Baseline ASAS-NSAID} - \text{Observed ASAS-NSAID}}{\text{Baseline ASAS-NSAID}}$ Proportion of patients with at least 50% decrease from baseline in ASAS-NSAID score. Derivation only applies to patients whose ASAS-NSAID is not equal to 0 at baseline.	
	ASAS-NSAID 10	Proportion of patients with ASAS-NSAID score <10	
	ASAS-NSAID 0	Proportion of patients with ASAS-NSAID score = 0	

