Mobility related measures	BASMI linear (incl. 5 components); chest expansion, occiput to wall distance change from baseline	MMRM	ITT Population	IXE80Q4W vs. placebo at Week 16 and all other postbaseline visits in Period 2	Other secondary efficacy analyses (Section 6.9.4).
		Descriptive statistics of change from baseline	Extended Treatment Period Population	No comparison during Period 3	Other secondary efficacy analyses (Section 6.9.4).
Enthesitis Scores	MASSES change from baseline	MMRM	ITT Population with Baseline MASSES >0	IXE80Q4W vs. placebo at Week 16 and all other postbaseline visits in Period 2	Other secondary efficacy analyses (Section 6.9.4).
		Descriptive statistics of change from baseline	Extended Treatment Period Population with Baseline MASSES >0	No treatment group comparisons during Period 3	Other secondary efficacy analyses (Section 6.9.4).

Measure	Variable	Analysis Method (Sections 6.1, 6.3)	Population (Section 6.1.5)	Comparison/Time Point	Analysis Type
	MASES score = 0	Logistic regression analysis with NRI; Fisher's exact test with NRI	ITT Population with Baseline MASES >0	IXE80Q4W vs. placebo at Week 16 and all other postbaseline visits in Period 2	Other secondary efficacy analyses (Section 6.9.4).
		Descriptive statistics of MASES = 0	Extended Treatment Period Population with Baseline MASES >0	No comparison during Period 3	Other secondary efficacy analyses (Section 6.9.4).
	Heel Enthesitis Score = 0	Logistic regression analysis with NRI; Fisher's exact test with NRI	ITT Population with Baseline Heel Enthesitis Score >0	IXE80Q4W vs. placebo at Week 16 and all other postbaseline visits in Period 2	Other secondary efficacy analyses (Section 6.9.4).
		Descriptive statistics of MASES = 0	Extended Treatment Period Population with Baseline Heel Enthesitis Score >0	No comparison during Period 3	Other secondary efficacy analyses (Section 6.9.4).
NSAID (including COX-2 inhibitors) Intake	Proportion of patients taking NSAID (including COX-2 inhibitors)	Descriptive statistics	Extended Treatment Period Population	At Weeks 16, 20, 24, 28, 32, 36, 44, 52.	Analyses on NSAID intake (Section 6.9.4.1)

Measure	Variable	Analysis Method (Sections 6.1, 6.3)	Population (Section 6.1.5)	Comparison/Time Point	Analysis Type
	Change from baseline in ASAS-NSAID	Descriptive statistics	Extended Treatment Period Population who have NSAID (including COX-2 inhibitor) intake at baseline	At Weeks 16, 20, 24, 28, 32, 36, 44, 52.	Analyses on NSAID intake (Section 6.9.4.1)

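### The logistic model for MASES = 0 omits the baseline MASES count, although the MMRM for MASES change in the same patients adjusts for it (minor; some loss of power, no loss of validity)

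*SAP*

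**What the plan says.** SAP Table RHCH.6.3 describes a MASES of 0 as full clearance ("MASES score = 0 refers to complete resolution in enthesitis") and limits the analysis to patients who have something to clear: "Analysis of MASES score = 0 only applies to patients with baseline enthesitis (MASES >0"). MASES is a count over 13 sites, each scored 0 or 1.

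Table RHCH.6.4 names the set as "ITT Population with Baseline MASES >0" and assigns logistic regression with nonresponder imputation and Fisher's exact test, at Week 16 and the other postbaseline visits of Period 2. SAP 6.1.1 gives the model: "logistic regression analysis with treatment, baseline CRP status, and TNF inhibitors experience (if applicable) in the model". SAP 6.2 brings in the baseline value only for MMRM and ANCOVA, so the baseline count is absent from this responder model.

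In the same table and the same population, MASES change from baseline is analysed by MMRM. SAP 6.1.1 puts the baseline value and its interaction with visit in that model.

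SAP 5.2 stratifies randomisation by CRP and TNF inhibitor experience, not by enthesitis. SAP 6.9.4 applies no multiplicity adjustment to other secondary efficacy analyses, and Table RHCH.6.4 places MASES = 0 among them.

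**The concern.** To reach 0, a patient with one active site needs that site to clear. A patient with eight needs all eight to clear. Baseline count is therefore likely to be one of the stronger predictors of this response, and it is known for everyone in the set, because a baseline MASES above 0 is the entry condition.

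Leaving a strong predictor out of a logistic model has three consequences in a randomised comparison. Power is lower than it need be. The odds ratio sits closer to 1 than the one conditional on baseline count. Any chance difference in baseline counts between the arms stays in the estimate. The third matters somewhat more here because the analysis set is a subset of about 140 randomised patients and is not balanced by design on enthesitis.

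The SAP also treats two analyses of one score in one population differently, without giving a reason.

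**Working it through.** **The plan's own figure.** The documents give none for MASES = 0. The power calculation behind the sample size (Protocol 10.1) concerns ASAS40: 44% vs 16%, 61 per arm, two-sided Fisher's exact test at 0.05. Full enumeration gives 90.5% power at 61 per arm and 89.9% at 60, so that figure reproduces. It says nothing about this endpoint.

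**Inputs that must be assumed.** The documents give no baseline MASES distribution, no site resolution rate and no size for the subset with MASES above 0. I take 25 to 50 patients per arm, which is 25/70 = 36% to 50/70 = 71% of the roughly 70 per arm.

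**Step 1: how strongly count predicts response.** If each active site clears independently with probability q and no new site appears, P(MASES = 0 | count k) = q^k.

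| k | q = 0.6 | q = 0.8 |
|---|---|---|
| 1 | 0.60 | 0.80 |
| 2 | 0.36 | 0.64 |
| 3 | 0.22 | 0.51 |
| 4 | 0.13 | 0.41 |
| 8 | 0.02 | 0.17 |

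With 2% new activity at each initially clear site, the value at k = 1 and q = 0.6 falls to 0.6 × 0.98^12 = 0.47. The gradient remains.

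**Step 2: effect of a chance imbalance.** Take q = 0.6 in both arms, so there is no treatment effect, and counts of 1 or 3 only. Suppose 50% of one arm and 60% of the other have count 1.
- First arm: 0.5 × 0.60 + 0.5 × 0.216 = 0.408, odds 0.408/0.592 = 0.689.
- Second arm: 0.6 × 0.60 + 0.4 × 0.216 = 0.446, odds 0.446/0.554 = 0.806.
- Odds ratio: 0.806/0.689 = 1.17, from the imbalance alone.

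**Step 3: power with and without the count.** The SAP model (treatment, CRP, TNF) was simulated 4000 times per setting, with site resolution of 0.5 on placebo and 0.7 on active treatment. Counts were either mostly low (40% at count 1) or spread evenly over 1 to 10. Sites were independent or correlated within patient (ICC 0.3).

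| Counts, sites | Per arm | Power without count | Power with count | Median log OR without, with |
|---|---|---|---|---|
| low, independent | 25 | 28.6% | 32.6% | 0.91, 1.14 |
| low, independent | 40 | 44.8% | 51.2% | 0.89, 1.10 |
| low, correlated | 25 | 31.4% | 33.4% | 0.90, 1.02 |
| low, correlated | 40 | 48.6% | 51.2% | 0.92, 1.01 |
| spread, independent | 25 | 12.0% | 15.0% | 1.06, 1.57 |
| spread, independent | 40 | 29.0% | 37.6% | 1.02, 1.43 |
| spread, correlated | 25 | 29.2% | 31.4% | 1.03, 1.16 |
| spread, correlated | 40 | 49.8% | 52.0% | 1.05, 1.16 |

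The gains here are 2.0 to 8.6 points, and 2.0 to 2.6 points when sites are correlated. With a larger effect (30% vs 70%), a different count distribution and log count as covariate, power rose from 50% to 61% and from 12% to 15% at 30 per arm, and from 67% to 75% and from 24% to 25% at 40 per arm. Over a wider set of assumptions at 25 to 50 per arm, the gain was about 1 to 13 points.

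**Step 4: validity.** With equal resolution in both arms (0.6 vs 0.6), the MASES = 0 test rejected in 2% to 6% of runs both with and without the count. Omitting it does not inflate type I error.

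**The case against.** The strongest reply is that this is a preference about one supportive model. Treatment is randomised and assessment is blinded, so the unadjusted comparison is valid. The enthesitis endpoint named in the objectives is change in MASES, which is already adjusted for baseline. No binary endpoint in the SAP is adjusted for its baseline value, so changing one makes its odds ratio conditional on something the others are not. SAP 6.9.6 allows extra covariates to be explored. All of this is correct, and it is why the point is minor. It does not remove the point: the exploratory clause is optional and does not name MASES, SAP 6.12.1 plans subgroup analyses for ASAS40 and ASAS20 only, and no planned output shows MASES = 0 by baseline count.

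Three stronger readings are tempting and do not hold.

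- A reader might fault the adjacent thresholds (above 0 to enter, 0 to respond). An endpoint defined as complete resolution needs exactly these. That a single site changing makes a responder is true only for a patient with one active site at baseline and no new one.
- A reader might infer a biased or anti-conservative test. Step 4 shows no inflation, and scoring noise falls on both blinded arms alike.
- A reader might extend the covariate to the heel endpoint, which has the same entry rule ("Analysis of Heel Enthesitis score = 0 only applies to patients with baseline Heel Enthesitis score >0"). Heel has two sites, so baseline is only 1 or 2. Adding it gained about 1 point at 25 to 40 per arm, gave no consistent gain at 20 per arm (-1 to +2 points), and lowered power by 7 to 8 points at 12 per arm.

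**Conclusion.** The point holds for the MASES = 0 logistic model only. The text establishes two facts: any baseline MASES above 0 qualifies, and the model leaves out a baseline count that the companion MMRM uses. That the count predicts strongly is an inference from the structure of the score. It is firm if sites resolve independently and weaker if they move together.

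The cost is about 1 to 13 points of power at 25 to 50 per arm, near the low end (2.0 to 2.6 points in the settings tabulated) with correlated sites, plus an attenuated odds ratio and uncorrected chance imbalance. Every figure rests on assumed counts, resolution rates and subset sizes, because the documents supply none. The unadjusted odds ratio is not an error: it is a different, less conditional quantity.

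The primary endpoint and the alpha-controlled family are untouched.

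**What to change.** In Table RHCH.6.4, on the MASES = 0 row, state that the Period 2 logistic model also includes baseline MASES as a covariate, for example log count. Keep Fisher's exact test with nonresponder imputation as listed there, and as the fallback that SAP 6.1.1 already provides when sparse data prevent the logistic model from giving a result. Leave the thresholds above 0 and at 0 as they are.

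Leave the heel model unchanged. At most, tabulate heel response by baseline score 1 vs 2.

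The cost is a line of SAP wording and one extra model term. The value is already collected and is present for every patient in the set. The small downside is that this odds ratio becomes conditional on baseline count, unlike those for the other binary endpoints, so a footnote should say so.

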
Secondary
 
The major secondary objectives are:
 
 To compare ixekizumab 80 mg Q4W to placebo in overall study population at Week 16 
Other secondary objectives are:
 
 To compare ixekizumab regimen 80 mg Q4W to placebo during the 16-week placebo-controlled period (Period 2) in overall study population 	
 Proportion of patients achieving an ASAS40 response Proportion of patients achieving an ASAS20 response Change from baseline in Ankylosing Spondylitis Disease Activity Score (ASDAS) Change from baseline in Bath Ankylosing Spondylitis Disease Activity Index (BASDAI) Change from baseline in Bath Ankylosing Spondylitis Functional Index (BASFI) Proportion of patients achieving ASDAS < 2.1 Change from baseline in magnetic resonance imaging (MRI) of the spine (Spondyloarthritis Research Consortium of Canada [SPARCC] score) Change from baseline in Short Form 36 (SF-36) physical component score (PCS) Proportion of patients who achieve ASAS20, ASAS40, ASAS 5/6, and partial remission by ASAS criteria Change from baseline in the individual components of the ASAS criteria Change from baseline in BASDAI Proportion of patients reaching BASDAI50 Change from baseline in ASDAS Proportion of patients who experience clinically-important improvement (change of ASDAS from baseline ≥ 1.1) or major improvement (change of ASDAS from baseline ≥ 2.0 or achievement of the lowest possible score) or inactive disease (ASDAS score < 1.3) Change from baseline in the measure of high sensitivity C-reactive protein (CRP) Change from baseline in BASFI Change from baseline in mobility 
 Bath Ankylosing Spondylitis Metrology Index (BASMI) (linear) and individual components Chest expansion Change from baseline in occiput to wall distance

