7.2. Method of Treatment Assignment

Patients who meet all criteria for enrollment will be randomized to double-blind treatment at Week 0 (Visit 2). Assignment to treatment groups will be determined by a computer-generated random sequence using an interactive web-response system (IWRS). The IWRS will be used to assign double-blind investigational product to each patient. Site personnel will confirm that they have located the correct assigned investigational product package by entering a confirmation number found on the package into the IWRS.

To achieve between-group comparability, the randomization will be stratified by baseline CRP (non-elevated or elevated) and TNF inhibitor experienced or naïve. The study will enroll approximately 60% of patients with baseline CRP elevated (>5.00 mg/L) and approximately 40% of patients with non-elevated baseline CRP. At least 61 bDMARD-naïve patients will be enrolled per arm.

Once a specific stratum is fully enrolled, the sponsor may stop further enrollment of patients fitting the criteria of that stratum.

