When the MMRM is used, the model will include treatment, baseline CRP status, TNF inhibitors experience, baseline value, baseline value-by-visit, visit, and treatment-by-visit interaction as fixed factors (except for the analysis of CRP, see paragraph below). The covariance structure to model the within-patient errors will be unstructured. If the unstructured covariance matrix results in a lack of convergence, the heterogeneous Toeplitz covariance structure, followed by the heterogeneous autoregressive covariance structure, followed by the compound symmetry, will be used. This order is specified according to a decreasing number of covariance parameters in the structure. The Kenward-Roger method will be used to estimate the denominator degrees of freedom. The restricted maximum likelihood (REML) will be used. Type III tests for the least-squares (LS) means will be used for the statistical comparison; the 95% CI will also be reported. Treatment group comparison with placebo at Week 16 (Visit 8) and all other visits will be reported.

For the analysis of CRP, the MMRM model will include treatment, baseline CRP status, TNF inhibitors experience, visit, and treatment-by-visit interaction as fixed factors.

When the ANCOVA is used, the model will include treatment, baseline CRP status, TNF inhibitors experience, and baseline value. Type III sums of squares for the LS means will be used for the statistical comparison; the 95% CI will also be reported.

For variables that are not collected at each postbaseline visit, data may exist at visits where the variable was not scheduled to be collected, due to early discontinuation visits. In these situations, data from the early discontinuation visit that do not correspond to the planned collection schedule will be excluded from the MMRM analyses (Andersen and Millen 2013). However, the data will still be used in other analyses, including shift analyses, or modified baseline observation carried forward (mBOCF) endpoint analyses, and other categorical analyses.

For selective efficacy measures, percent improvement will be calculated as $100 \times (\text{baseline score} - \text{observed scores}) / \text{baseline score}$, unless specified otherwise. If a patient has experienced an improvement, this measure will be positive. If a patient has experienced a worsening, this measure will be negative.

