Bath Ankylosing Spondylitis Functional Index (BASFI): The BASFI establishes a patient's functional baseline and subsequent response to treatment (Calin et al. 1995). To complete the BASFI, a patient will be asked to rate the difficulty associated with 10 individual basic functional activities. Patients respond to each question using a NRS (range 0 to 10), with a higher score indicating worse functioning.	BASFI score BASFI change from baseline – major secondary outcome	BASFI score is the mean of the 10 item scores completed on a NRS Range: 0 to 10 "0" (easy) and "10" (impossible).	Missing if >20% scores (ie, >2 of the 10 item scores) are missing
High Sensitivity C-Reactive Protein (CRP):	CRP value	Lab values obtained from central lab	Missing if missing

Measure / Description	Variable	Derivation / Comment	Imputation Approach if with Missing Components
High sensitivity CRP will be the measure of acute phase reactant. It will be measured with a high sensitivity assay at the central laboratory to help assess the effect of ixekizumab on disease activity.			

Measure / Description	Variable	Derivation / Comment	Imputation Approach if with Missing Components												

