Ankylosing Spondylitis Disease Activity Score (ASDAS): The ASDAS is a composite index to assess disease activity in AS (Machado et al. 2011a, 2011b; Zochling 2011). The parameters used for the ASDAS (with CRP as acute phase reactant): 1) Total back pain (BASDAI Q2) 2) Patient global 3) Peripheral pain/swelling (BASDAI Q3) 4) Duration of morning stiffness (BASDAI Q6) 5) CRP in mg/L	ASDAS _{crp} ASDAS _{crp} change from baseline - major secondary outcome	ASDAS _{crp} (Sieper et al. 2009): $0.121 \times \text{total back pain} + 0.110 \times \text{patient global} + 0.073 \times \text{peripheral pain/swelling} + 0.058 \times \text{duration of morning stiffness} + 0.579 \times \text{Ln}(\text{CRP}+1)$ (Machado et al. 2015). C-reactive protein is in mg/liter, the range of other variables is from 0 to 10; Ln represents the natural logarithm.	Missing if any of the components is missing. If CRP <2 mg/L or below the limit of detection, then use 2 mg/L in the calculation (Machado et al. 2015).

Measure / Description	Variable	Derivation / Comment	Imputation Approach if with Missing Components
	ASDAS Disease Activity States	Four (4) disease activity states have been defined by ASAS consensus (Machado et al. 2011c, Machado 2018): 
 • ASDAS <1.3 defines inactive disease • $1.3 \leq \text{ASDAS} < 2.1$ defines low disease activity • $2.1 \leq \text{ASDAS} \leq 3.5$ defines high disease activity • ASDAS >3.5 defines very high disease activity. 	Set the disease activity state to worst state (ie, very high) if observed ASDAS score is missing
	ASDAS<2.1	Defined as ASDAS <2.1 (low or inactive disease activity)	
	Clinical important improvement	Defined as at least 1.1 unit change in ASDAS from baseline	Missing if baseline or observed ASDAS score is missing
	Major improvement	Defined as at least 2.0 unit change in ASDAS from baseline or reached the minimum of ASDAS score (0.6361) at postbaseline visit	

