SPARCC SIJ Structural Score (SSS)	SPARCC SIJ SSS score change from baseline for each of the 4 features: fat metaplasia, bone erosion, backfill and ankylosis.	ANCOVA with observed case analysis; ANCOVA with mBOCF	ITT Population	IXE80Q4W vs. placebo at Week 16	Other secondary efficacy analyses (Section 6.9.4).
		Descriptive statistics of change from baseline	Extended Treatment Period Population	No comparisons at Week 52	Other secondary efficacy analyses (Section 6.9.4).
ASAS	ASAS5/6 and ASAS partial remission	Logistic regression analysis with NRI; Fisher's exact test with NRI	ITT Population	IXE80Q4W vs. placebo at Week 16 and all other postbaseline visits in Period 2	Other secondary efficacy analyses (Section 6.9.4).
		Descriptive statistics of ASAS5/6 response rate and ASAS partial remission	Extended Treatment Period Population	No comparison during Period 3	Other secondary efficacy analyses (Section 6.9.4).
Patient Global	Patient Global change and % improvement from baseline	MMRM	ITT Population	IXE80Q4W vs. placebo at Week 16 and all other postbaseline visits in Period 2	Other secondary efficacy analyses (Section 6.9.4).
		Descriptive statistics of change from baseline	Extended Treatment Period Population	No comparison during Period 3	Other secondary efficacy analyses (Section 6.9.4).
Spinal Pain	Spinal Pain and Spinal Pain at night change and % improvement from baseline	MMRM	ITT Population	IXE80Q4W vs. placebo at Week 16 and all other postbaseline visits in Period 2	Other secondary efficacy analyses (Section 6.9.4).
		Descriptive statistics of change from baseline	Extended Treatment Period Population	No comparison during Period 3	Other secondary efficacy analyses (Section 6.9.4).

Measure	Variable	Analysis Method (Sections 6.1, 6.3)	Population (Section 6.1.5)	Comparison/Time Point	Analysis Type
CRP	CRP change from baseline	MMRM	ITT Population; ITT Population in bDMARD-naïve patients; Per Protocol Set; Per Protocol Set in bDMARD-naïve patients	IXE80Q4W vs. placebo at Week 16 and all other postbaseline visits in Period 2	Other secondary efficacy analyses (Section 6.9.4).
		Descriptive statistics of change from baseline	Extended Treatment Period Population	No comparison during Period 3	Other secondary efficacy analyses (Section 6.9.4).

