6.9.4. Other Secondary Efficacy Analyses

There will be no adjustment for multiple comparisons for other secondary efficacy analyses.

The other secondary efficacy variables for secondary objectives will be done on:

- ASAS40, ASAS20, ASAS5/6 and partial remission, BASDAI50
- ASDAS inactive disease, ASDAS<2.1, clinically important improvement and major improvement
- Change from baseline in:
 - individual components of the ASAS criteria (patient global, spinal pain, function, inflammation, CRP, and spinal mobility [lateral spinal flexion])
 - BASDAI and inflammation (mean of Q5 and Q6 on BASDAI)
 - ASDAS, BASFI, CRP
 - mobility (BASMI linear and individual components, chest expansion, occiput to wall distance)
 - MRI SPARCC spine score; MRI SPARCC SIJ structural score (SSS) for each of the 4 features: fat metaplasia, bone erosion, backfill and ankyloses; MRI SPARCC SIJ score; enthesitis score (MASES)
 - ASAS-NSAID score (apply to Period 3 analysis only, Section 6.9.4.1)

Treatment comparisons of ixekizumab treatment group and placebo at Week 16 (Visit 8) and all other postbaseline visits during Period 2 will be provided.

Descriptive statistics (that is, no inferential testing) will be provided during Period 3, or Combined Periods 2 and 3, as applicable.

Table RHCH.6.4 provides the detailed analyses including analysis type, method and imputation, population, time point, and treatment comparisons for other secondary outcomes.

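### Change in CRP is compared in mg/L by an MMRM that also omits continuous baseline CRP; a log-scale model with log baseline would be more powerful, by an amount the documents do not determine

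*SAP*

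**What the plan says.** Protocol Section 4 and SAP Section 4 list change from baseline in high-sensitivity CRP among the other secondary endpoints. SAP Section 6.9.4 says of that group: "There will be no adjustment for multiple comparisons for other secondary efficacy analyses".

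Four SAP statements fix the analysis:
- **Variable.** Table RHCH.6.3 describes the CRP value as "Lab values obtained from central lab". No transformation is stated.
- **Change.** Section 6.1.1: "Change from baseline will be calculated as the visit value of interest minus the baseline value".
- **Comparison.** Table RHCH.6.4 has "CRP change from baseline" by MMRM, ixekizumab against placebo, at Week 16 and every other post-baseline visit in Period 2. It is done in the ITT population, the per-protocol set and the bDMARD-naïve part of each.
- **Model terms.** Section 6.1.1: "For the analysis of CRP, the MMRM model will include treatment, baseline CRP status, TNF inhibitors experience, visit, and treatment-by-visit interaction as fixed factors".

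The last item is an exception made for CRP only. The general MMRM in Protocol Section 10.3.1 and SAP Section 6.1.1 carries the baseline value and its interaction with visit, and SAP Section 6.2 gives that as the general rule. The SAP gives no reason for the exception.

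Within ASDAS the SAP handles CRP differently. Table RHCH.6.3 enters it as Ln(CRP+1) ("Ln represents the natural logarithm") and replaces values under 2 mg/L by 2 mg/L. Neither document plans a log, ratio or rank analysis of CRP itself, even as a sensitivity analysis.

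**The concern.** A laboratory marker that cannot fall below zero and has no upper limit tends to vary in proportion to its level. In mg/L, a patient who starts high can change far more than one who starts near 5 mg/L, so a few patients can drive both the mean difference and its standard error. The log scale evens this out.

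The missing baseline term makes it worse. The only adjustment for starting level is a dichotomy at 5.00 mg/L, so all the variation in baseline within the elevated group stays in the residual of the change score.

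At stake is the precision of the only stand-alone blood marker among the secondary efficacy endpoints. A real proportional fall in CRP could be reported with a wide interval. A log analysis added only after the raw result is known would look data-driven.

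**Working it through.** **The plan's own figures.** The only stated power basis is ASAS40 by two-sided Fisher's exact test at 0.05. Exact enumeration gives 90.5% for 44% vs 16% with 61 per arm, and 93.2% for 42% vs 15% with 70 per arm. Both agree with Protocol Section 10.1. Nothing comparable is stated for CRP.

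**Inputs from the documents.** 70 per arm, 1:1 (Protocol 5.2 and 10.1), and the split at 5 mg/L in Protocol 7.2: "The study will enroll approximately 60% of patients with baseline CRP elevated (>5.00 mg/L) and approximately 40% of patients with non-elevated baseline CRP".

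**Assumptions, not in the documents.** Log-normal CRP; SD σ of ln(CRP) from 0.8 to 1.4; baseline to Week 16 log correlation 0.5 to 0.7; ixekizumab/placebo ratio of geometric means 0.3 to 0.8; about 13% TNF-experienced, all with elevated CRP; complete data; no floor for low values.

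**What the 60/40 split fixes.** If 60% lie above 5 mg/L, the log mean is μ = ln 5 + 0.2533σ, and the upper 97.5% point is exp(μ + 1.96σ):
- σ = 0.8: median 6.1 mg/L, upper point 29 mg/L
- σ = 1.0: median 6.4 mg/L, upper point 46 mg/L
- σ = 1.4: median 7.1 mg/L, upper point 111 mg/L

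The split is compatible with all of these, so it does not determine the skew.

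**Models.** Week 16 change was regressed on treatment, CRP status and TNF experience, as a stand-in for the Week 16 MMRM contrast, which it approximates with complete data. Four versions were compared: raw change as planned; raw change plus raw baseline; log change with the planned factors; log change plus log baseline. Tests were two-sided at 0.05. With 1,500 replicates the simulation standard error is at most √(0.25/1500) = 1.3 percentage points.

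**Mid-range setting** (σ = 1.0, correlation 0.6, ratio 0.6):

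| Effect | Raw, as planned | Raw + baseline | Log | Log + log baseline |
|---|---|---|---|---|
| Same ratio in all patients | 55% | 79% | 95% | 97% |
| Only in patients with elevated CRP | 39% | 54% | 56% | 58% |

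Relative loss = 1 − (raw power / log power).
- Same ratio in all, planned factors on both scales: 1 − 55/95 = 42%. With baseline in both: 1 − 79/97 = 19%. Of the 97 − 55 = 42 points between the first and last models, 79 − 55 = 24 come from the baseline term alone.
- Effect only in elevated CRP, planned factors: 1 − 39/56 = 30%. With baseline in both: 1 − 54/58 = 7%. Of the 58 − 39 = 19 points, 54 − 39 = 15 come from the baseline term.

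**Range, planned factors on both scales, same ratio in all patients.**

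| σ | Correlation | Ratio | Raw | Log | Loss |
|---|---|---|---|---|---|
| 0.8 | 0.7 | 0.5 | 97% | 100% | 3% |
| 1.0 | 0.5 | 0.4 | 84% | 100% | 16% |
| 1.0 | 0.5 | 0.5 | 68% | 99.5% | 32% |
| 1.0 | 0.5 | 0.7 | 30% | 64% | 53% |
| 1.4 | 0.5 | 0.6 | 18% | 65% | 72% |

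Across all settings the loss runs from about 0% (small spread, large effect) to about 70% (large spread). With no effect, the planned model rejected in 2.6% to 5.5% of simulated trials.

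**The case against.** The strongest reply is that the scale is being blamed for a covariate problem. This largely stands. Keeping mg/L and restoring the baseline value that the protocol's MMRM contains recovers more than half of the gap in the mid-range setting, and most of it if only patients with elevated CRP respond. A reader might infer that the mg/L scale by itself costs a third to half of the power. The calculations do not support that: such losses arise in part of the assumed range, and mostly from scale and omitted baseline together.

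Second, the simulation favours logs, because it assumes exact log-normality and, in its main form, the same proportional fall in the roughly 40% of patients without elevated CRP. This also stands, which is why the second scenario is shown. The log model still does no worse there, but its advantage over raw plus baseline is small.

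Third, a mg/L difference is directly readable, follows the SAP's definition of change, and keeps its type I error. It would therefore be wrong to say that the planned scale has no benefit or that the test is invalid.

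Fourth, little depends on it. The endpoint is unadjusted and outside the graphical procedure. Log CRP already enters two major secondary endpoints through ASDAS, MRI of the spine is another objective measure, and the descriptive summaries include medians. This limits the importance of the point. It does not make the planned CRP model a good one, since ASDAS mixes CRP with four patient-reported items.

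**Conclusion.** The point holds in a limited form. The planned CRP comparison uses an untransformed scale and leaves out continuous baseline CRP, contrary to the protocol's general model and without explanation. Either feature can cost power; neither threatens validity.

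The size is uncertain: about 0% to 70% of the power of a log model with the same factors, depending on a CRP spread, correlation and effect that the documents do not give. A reader might take strong skew as documented. It is not: a 60/40 split at 5 mg/L does not establish it, and the logarithm in ASDAS only suggests it. How the loss divides between scale and baseline depends on whether patients with normal CRP also respond.

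No primary or major secondary conclusion changes. This is a low-cost improvement to an other secondary endpoint.

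**What to change.** Before unblinding, replace the CRP sentence in SAP Section 6.1.1 and adjust the CRP rows of Tables RHCH.6.3 and RHCH.6.4:
- Analyse Period 2 CRP by MMRM on change in ln(CRP), or in Ln(CRP+1) to match ASDAS. Add log baseline and log-baseline-by-visit to the existing factors, with the +1 in the baseline term too if that form is chosen.
- State the rule for values that are low or below the limit of quantification, and say whether the 2 mg/L floor used for ASDAS applies here.
- Report the ixekizumab/placebo ratio of geometric means with 95% CI. If Ln(CRP+1) is used, say that the ratio refers to CRP+1.
- Keep the mg/L summaries as descriptive output.

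The cost is a short SAP edit and one derived variable; no new data are needed. The downside is that the inferential estimate becomes a ratio instead of a mg/L difference. If the sponsor prefers mg/L, restoring baseline and baseline-by-visit, or giving the reason for omitting them, is the minimum change.
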